11.2 Methods for Evaluation of Disease

All measurements should be taken and recorded in metric notation using a ruler, calipers, or a digital measurement tool. All baseline evaluations should be performed as closely as possible to the beginning of treatment and never more than 4 weeks before the beginning of the treatment.

The same method of assessment and the same technique should be used to characterize each identified and reported lesion at baseline and during follow-up. Imaging-based evaluation is preferred to evaluation by clinical examination unless the lesion(s) being followed cannot be imaged but are assessable by clinical exam.

Clinical lesions. Clinical lesions will only be considered measurable when they are superficial (*e.g.*, skin nodules and palpable lymph nodes) and ≥ 10 mm in diameter as assessed using calipers (*e.g.*, skin nodules). In the case of skin lesions, documentation by color photography, including a ruler to estimate the size of the lesion, is recommended.

Chest x-ray. Lesions on chest x-ray are acceptable as measurable lesions when they are clearly defined and surrounded by aerated lung; however, CT is preferable.

CT scans. This guideline has defined measurability of lesions on CT scan based on the assumption that CT thickness is 5mm or less. If CT scans have slice thickness greater than 5 mm, the minimum size of a measurable lesion should be twice the slice thickness.

MRI scans with “thin cuts.” MRI is required for assessment of brain metastases with **slices of 2mm or less. Because this study allows a minimum lesion size of 5mm in the brain, all brain MRIs must be performed with “thin cuts” (slice thickness required to be no greater than 2 mm).** MRI also appropriate in certain additional situations (*e.g.* for extremities). The technical specifications of the scanning sequences used should be optimized for the evaluation of the type and site of disease. Furthermore, as with CT, the modality used at follow-up should be the same as was used at baseline and the lesions should be measured/assessed on the same pulse sequence. It is beyond the scope of the RECIST guidelines to prescribe specific MRI pulse sequence parameters for all scanners, body parts, and diseases. Ideally, the same type of scanner should be used and the image acquisition protocol should be followed as closely as possible to prior scans. Body scans should be performed with breath-hold scanning techniques, if possible.

FDG-PET. While FDG-PET response assessments need additional study, it is sometimes reasonable to incorporate the use of FDG-PET scanning to complement CT scanning in assessment of progression (particularly possible 'new' disease). New lesions on the basis of FDG-PET imaging can be identified according to the following algorithm:

- (a) Negative FDG-PET at baseline, with a positive FDG-PET at follow-up is a sign of PD based on a new lesion.
- (b) No FDG-PET at baseline and a positive FDG-PET at follow-up: If the positive FDG-PET at follow-up corresponds to a new site of disease confirmed by CT, this is PD. If the positive FDG-PET at follow-up is not confirmed as a new site of disease

on CT, additional follow-up CT scans are needed to determine if there is truly progression occurring at that site (if so, the date of PD will be the date of the initial abnormal FDG-PET scan). If the positive FDG-PET at follow-up corresponds to a pre-existing site of disease on CT that is not progressing on the basis of the anatomic images, this is not PD.

(c) FDG-PET may be used to upgrade a response to a CR in a manner similar to a biopsy in cases where a residual radiographic abnormality is thought to represent fibrosis or scarring. The use of FDG-PET in this circumstance should be prospectively described in the protocol and supported by disease-specific medical literature for the indication. However, it must be acknowledged that both approaches may lead to false positive CR due to limitations of FDG-PET and biopsy resolution/sensitivity.

Note: A 'positive' FDG-PET scan lesion means one which is FDG avid with an uptake greater than twice that of the surrounding tissue on the attenuation corrected image.

PET-CT. At present, the low dose or attenuation correction CT portion of a combined PET-CT is not always of optimal diagnostic CT quality for use with RECIST measurements. However, if the site can document that the CT performed as part of a PET-CT is of identical diagnostic quality to a diagnostic CT (with IV and oral contrast), then the CT portion of the PET-CT can be used for RECIST measurements and can be used interchangeably with conventional CT in accurately measuring cancer lesions over time. Note, however, that the PET portion of the CT introduces additional data which may bias an investigator if it is not routinely or serially performed.

MIBG (meta-iodobenzylguanidine). The following is recommended, to assure high quality images are obtained.

Patient preparation: Iodides, usually SSKI (saturated solution of potassium iodide), are administered to reduce thyroidal accumulation of free radioiodine, preferably beginning the day prior to injection and continuing for 3 additional days (4 days total). For infants and children, one drop t.i.d. is sufficient, for adolescents 2 drops t.i.d., and for adults 3 drops t.i.d. Participants and/or parents are asked about exposure to potential interfering agents. If none is noted, an indwelling intravenous line is established. The dose of MIBG is administered by slow intravenous injection over 90 seconds.

Images from the head to the distal lower extremities should be obtained.

I-123MIBG scintigraphy is performed to obtain both planar and tomographic images.

Planar: Anterior and posterior views from the top of the head to the proximal lower extremities are obtained for 10 minutes at 24 hours and occasionally at 48 hours following injection of 10 mCi/1.7 square meters of body surface area (~150 μ Ci/kg, maximum 10 mCi). Anterior views of the distal lower extremities are adequate. A

large field of view dual head gamma camera with low energy collimators is preferred.

SPECT: Most participants receiving I-123 MIBG also undergo SPECT at 24 hours, using a single or multi-headed camera with a low energy collimator. The camera is rotated through 360 degrees, 120 projections at 25 seconds per stop. Data are reconstructed using filtered back projections with a Butterworth filter and a cut off frequency of 0.2-0.5. SPECT/CT may be performed at institutions with this capacity.

Ultrasound. Ultrasound is not useful in assessment of lesion size and should not be used as a method of measurement. Ultrasound examinations cannot be reproduced in their entirety for independent review at a later date and, because they are operator dependent, it cannot be guaranteed that the same technique and measurements will be taken from one assessment to the next. If new lesions are identified by ultrasound in the course of the study, confirmation by CT or MRI is advised. If there is concern about radiation exposure from CT, MRI may be used instead of CT in selected instances.

Endoscopy, Laparoscopy. The utilization of these techniques for objective tumor evaluation is not advised. However, such techniques may be useful to confirm complete pathological response when biopsies are obtained or to determine relapse in trials where recurrence following complete response (CR) or surgical resection is an endpoint.

Tumor markers. Tumor markers alone cannot be used to assess response. If markers are initially above the upper normal limit, they must normalize for a participant to be considered in complete clinical response.

Cytology, Histology. These techniques can be used to differentiate between partial responses (PR) and complete responses (CR) in rare cases (*e.g.*, residual lesions in tumor types, such as germ cell tumors, where known residual benign tumors can remain).

The cytological confirmation of the neoplastic origin of any effusion that appears or worsens during treatment when the measurable tumor has met criteria for response or stable disease is mandatory to differentiate between response or stable disease (an effusion may be a side effect of the treatment) and progressive disease.

11.3 Response Criteria: **modified RECIST version 1.1**

Response and progression will be evaluated in this study using the international criteria proposed by the Response Evaluation Criteria in Solid Tumors (RECIST) guideline (version 1.1);³⁹ however there will be **two modifications for assessment of brain lesions on this protocol:**

- 1) modification to allow up to five target lesions in the brain (all other organs continue to have a maximum of 2 target lesions), and the maximum number of target lesions globally may be up to 10 lesions.
- 2) to include target lesions in the brain measuring ≥ 5 mm in their longest diameter as seen on thin cut MRI (slice thickness ≤ 2 mm), as described previously in other brain

metastases trials.^{3,40,41}

Changes in the largest diameter (unidimensional measurement) of the tumor lesions and the shortest diameter in the case of malignant lymph nodes are used in the RECIST criteria.

Evaluation of Target Lesions

Complete Response (CR): Disappearance of all target lesions. Any pathological lymph nodes (whether target or non-target) must have reduction in short axis to <10 mm.

Partial Response (PR): At least a 30% decrease in the sum of the diameters of target lesions, taking as reference the baseline sum diameters.

Progressive Disease (PD): At least a 20% increase in the sum of the diameters of target lesions, taking as reference the smallest sum on study (this includes the baseline sum if that is the smallest on study). In addition to the relative increase of 20%, the sum must also demonstrate an absolute increase of at least 5 mm. (Note: the appearance of one or more new lesions is also considered progression).

Stable Disease (SD): Neither sufficient shrinkage to qualify for PR nor sufficient increase to qualify for PD, taking as reference the smallest sum diameters while on study.

Evaluation of Non-Target Lesions

Complete Response (CR): Disappearance of all non-target lesions. All lymph nodes must be non-pathological in size (<10 mm short axis).

Non-CR/Non-PD: Persistence of one or more non-target lesion(s).

Progressive Disease (PD): Appearance of one or more new lesions and/or *unequivocal progression* of existing non-target lesions. *Unequivocal progression* should not normally trump target lesion status. It must be representative of overall disease status change, not a single lesion increase.

Although a clear progression of “non-target” lesions only is exceptional, the opinion of the treating physician should prevail in such circumstances, and the progression status should be confirmed at a later time by the review panel (or Principal Investigator).

Evaluation of New Lesions

The finding of a new lesion should be unequivocal (i.e. not due to difference in scanning technique, imaging modality, or findings thought to represent something other than tumor (for example, some ‘new’ bone lesions may be simply healing or

flare of pre-existing lesions). However, a lesion identified on a follow-up scan in an anatomical location that was not scanned at baseline is considered new and will indicate PD. If a new lesion is equivocal (because of small size etc.), follow-up evaluation will clarify if it truly represents new disease and if PD is confirmed, progression should be declared using the date of the initial scan on which the lesion was discovered.

Evaluation of Best Overall Response

The best overall response is the best response recorded from the start of the treatment until disease progression/recurrence (taking as reference for progressive disease the smallest measurements recorded since the treatment started). The patient's best response assignment will depend on the achievement of both measurement and confirmation criteria.

Evaluation of BOR

Target Lesions	Non-Target Lesions	New Lesions*	Overall Response
CR	CR	No	CR
CR	Non-CR/Non-PD	No	PR
CR	Not evaluated	No	PR
PR	Non-CR/Non-PD/not evaluated	No	PR
SD	Non-CR/Non-PD/not evaluated	No	SD
PD	Any	Yes or No	PD
Any	PD**	Yes or No	PD
Any	Any	Yes	PD

* See RECIST 1.1 manuscript for further details on what is evidence of a new lesion.

** In exceptional circumstances, unequivocal progression in non-target lesions may be accepted as disease progression.

Note: Participants with a global deterioration of health status requiring discontinuation of treatment without objective evidence of disease progression at that time should be reported as “*symptomatic deterioration.*” Every effort should be made to document the objective progression even after discontinuation of treatment.

11.4 Duration of Response

Duration of overall response: The duration of overall response is measured from the time measurement criteria are met for CR or PR (whichever is first recorded) until the first

date that recurrent or progressive disease is objectively documented (taking as reference for progressive disease the smallest measurements recorded since the treatment started, or death due to any cause. Participants without events reported are censored at the last disease evaluation).

Duration of overall complete response: The duration of overall CR is measured from the time measurement criteria are first met for CR until the first date that progressive disease is objectively documented, or death due to any cause. Participants without events reported are censored at the last disease evaluation.

Duration of stable disease: Stable disease is measured from the start of the treatment until the criteria for progression are met, taking as reference the smallest measurements recorded since the treatment started, including the baseline measurements.

11.5 Progression-Free Survival

Progression-Free Survival: Progression-Free Survival (PFS) is defined as the time from randomization (or registration) to the earlier of progression in the intracranial or extracranial sites or death due to any cause. Herein, the term “PFS” refers to PFS in both the intracranial and extracranial compartments (global). The follow-up of participants alive without disease progression is censored at date of last disease evaluation.

Time to Progression: Time to Progression (TTP) is defined as the time from randomization (or registration) to progression, or censored at date of last disease evaluation for those without progression reported.

11.6 Response Review

Central review is not required.

12. DATA REPORTING / REGULATORY REQUIREMENTS

Adverse event lists, guidelines, and instructions for AE reporting can be found in Section 7.0 (Adverse Events: List and Reporting Requirements).

12.1 Data Reporting

Method

The DF/HCC Office of Data Quality (ODQ) will collect, manage, and perform quality checks on the data for this study.

Responsibility for Data Submission

Investigative sites are responsible for submitting data and/or data forms to the Office of Data Quality (ODQ) in accordance with DF/HCC policies.

12.2 Data Safety Monitoring

12.2.1 The DF/HCC Data and Safety Monitoring Board (DSMB) will review and monitor study progress, toxicity, safety and other data from the randomized portion of this study. The Board is chaired by a medical oncologist from outside of DF/HCC and its membership composed of internal and external institutional representation. Information that raises any questions about participant safety or protocol performance will be addressed by the Sponsor-Investigator, statistician and study team. Should any major concerns arise, the DSMB will offer recommendations regarding whether or not to suspend the study.

The DSMB will meet twice a year to review accrual, toxicity, response and reporting information. Information to be provided to the DSMB may include: participant accrual; treatment regimen information; all adverse events and serious adverse events reported across all sites by category; summary of any deaths on study; audit results; and a summary provided by the study team. Other information (e.g. scans, laboratory values) will be provided upon request.

12.2.2 The DF/HCC Data Safety Monitoring Committee (DSMC) will review and monitor study progress, toxicity, safety and other data from the safety run-in phase of this study. The DSMC meets monthly to review protocols and is chaired by a medical oncologist appointed by the Senior VP for Research. The DSMC will typically review a protocol every 3, 6, or 9 months based on protocol specifics. Information that raises any questions about participant safety or protocol performance will be addressed by the Sponsor-Investigator, statistician and study team. Should any major safety concerns or issues with data compliance arise, the DSMC will offer recommendations regarding whether or not to suspend the study.

12.3 Multi-Center Guidelines

This protocol will adhere to DF/HCC Policy MULTI-100 and the requirements of the DF/HCC Multi-Center Data and Safety Monitoring Plan. The specific responsibilities of the Sponsor-Investigator, Coordinating Center, and Participating Institutions and the procedures for auditing are presented in Appendix B.

12.4 Collaborative Agreements Language

N/A

13. STATISTICAL CONSIDERATIONS

13.1 Study Design/Endpoints

It was recently shown that patients with small asymptomatic brain metastases can be treated with medical therapy rather than upfront radiation therapy.³ The response rate in this study was 48% and the intracranial and the extracranial response rates were largely concordant. Progression-free survival at 6 months (PFS6) was 61%. However, many patients progressed within the first 6 months. Therefore, freedom from progression at the 6-month mark is a clinically important and

measurable outcome.

We propose a multi-center, double-blind, randomized, phase II signal-detection trial with a non-randomized safety run-in to assess the efficacy and safety of adding troriluzole to ipilimumab/nivolumab induction and nivolumab maintenance in patients with melanoma that has metastasized to the brain. Patients will be randomly assigned in equal proportions to ipilimumab/nivolumab/placebo induction followed by nivolumab/placebo maintenance (INP) or ipilimumab/nivolumab/troriluzole induction followed by nivolumab/troriluzole maintenance (INT). The randomization will be stratified by prior BRAF-directed therapy (yes/no) and prior therapy with anti-PD-1 treatments (yes/no).

Safety Run-in: Up to three cohorts of patients will be treated in a 3+3 design with the triple drug combination to provide dosing information and an early assessment of safety. A starting dose of troriluzole at 140 mg/280 mg will be used; two fallback doses will also be investigated if the starting dose proves too toxic.

Cohort de-escalation table during safety run-in:

Dose Level	Troriluzole Dose
Starting cohort	140 mg PO QAM and 280 mg PO QPM
Cohort -1	140 mg PO BID
Cohort -2	140 mg PO daily
If ≥ 2 DLTs on Cohort -2	Permanently stop the trial

At the end of each cohort of the safety run-in, enrollment will pause for a comprehensive review of the safety data including dose-limiting toxicity (DLT). If fewer than two patients within a cohort have DLTs then that dose level will be considered the MTD and enrollment to the randomized trial will begin. If two or more patients within a safety cohort have DLTs, then the dose will either be de-escalated, or the trial will stop. A participant will be considered to have completed the DLT period with no dose limiting toxicities only if they have taken $\geq 80\%$ of their assigned Troriluzole doses in the DLT period, which is the first 6 weeks of treatment.

Following the Safety Run-in, all participants will be enrolled on the randomized portion of the study.

Primary Endpoint. The primary endpoint of the study is global progression-free survival in patients with melanoma brain metastases who are treated with INT vs. INP. Of particular interest will be PFS at 6 months.

PFS is defined as the time from random assignment to the earlier of death or documented disease progression in the intracranial or extracranial compartments. The follow-up of patients who have neither died nor progressed will be censored at the date of the last follow-up visit.

Secondary Endpoints. The secondary objectives and their associated endpoints evaluate other important clinical outcomes, including overall survival (OS), intracranial response rate (RR) and

PFS, extracranial RR and PFS, and safety (number of participants experiencing adverse events, particularly neurologic events). We will also investigate:

- tolerability (number of induction cycles administered, number of maintenance cycles administered)
- use of corticosteroids for management of symptomatic cerebral edema (number of participants)
- use of corticosteroids for management of immune related adverse events (number of participants who require prednisone ≥ 1 mg/kg or equivalent)
- frequency of clinically-indicated stereotactic radiation therapy to the brain on study (number of patients, number of instances and number of lesions irradiated)
- frequency of clinically-indicated surgical intervention to the brain on study (number of participants)

Planned subgroup analyses according to baseline characteristics:

- Prior anti-PD-1 exposure (yes vs. no – if yes then adjuvant vs. metastatic setting)
- Prior ipilimumab exposure (yes vs. no)
- Age (<65 years vs 65 years or older)
- ECOG (0 vs 1)
- LDH at baseline (normal vs. elevated)
- Number of brain metastases (<3 vs 3 or more)
- Brain-directed stereotactic radiation therapy prior to study entry (yes vs. no)
- Craniotomy prior to study entry (yes vs. no)

Planned subgroup analyses according to on-study events:

- On-study brain-directed stereotactic radiation therapy (yes vs. no)

Exploratory Endpoints:

- associations between BRAF/NRAS mutation status and response endpoints, as well as tissue biomarker profiles between paired tissues from extracranial and intracranial metastases from individual patients, where available
- associations between peripheral blood immune cell subpopulations (which may include but is not limited to T-cell, NK, B-cell, MDSC, and serum soluble factors with clinical endpoints and/or the occurrence of adverse events)

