1. OBJECTIVES

1.1 Study Design

We propose a multi-center, blinded, randomized, phase II signal-detection trial with safety run-in to assess the efficacy and safety of adding troriluzole to ipilimumab + nivolumab in patients with melanoma that has metastasized to the brain.

There will be a Safety Run-in, which will be a single-arm, open-label 3+3 design in which all subjects will be treated with ipilimumab + nivolumab + troriluzole (INT). Following the Safety Run-in (Part I), all participants will be enrolled on the double-blind randomized portion of the study (Part II). Subjects will be randomly assigned in equal proportions to induction therapy with ipilimumab + nivolumab + placebo (INP) or ipilimumab + nivolumab + troriluzole (INT). Subjects assigned to the troriluzole vs. placebo arm will continue troriluzole or placebo in the maintenance period with nivolumab. The randomization will be stratified by prior therapy with BRAF-directed therapy (yes/no) and prior therapy with anti-PD-1 treatment (yes/no).

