5. TREATMENT PLAN

5.1 Treatment Regimen

Cycle length is variable during this protocol. During the induction phase, cycles are 3 weeks. During the maintenance phase, cycles are 4 weeks.

5.1.1 Safety Run-In:

The starting dose of the Safety Run-In is outlined below. Up to three cohorts of participants will be treated in a 3+3 design. At the end of each cohort accrual of 3 participants, enrollment will pause for a comprehensive review of the safety data including dose-limiting toxicity (DLT). A starting dose of Troriluzole at 140 mg/280 mg will be used. If there are ≥ 2 DLTs as defined in Section 6.2, the fallback dose in cohort -1 will be used for three new participants accrued to Cohort -1. If there are < 2 DLTs in the first three participants, an additional three participants will be added to the starting cohort. From this point, if fewer than two patients within a cohort have DLTs then that dose level will be considered the MTD and enrollment to the randomized trial will begin. If two or more patients within a safety cohort have DLTs, then the dose will either be de-escalated, or the trial will stop. A participant will be considered to have completed the DLT period with no dose limiting toxicities only if they have taken $\geq 80\%$ of their assigned Troriluzole doses in the DLT period, which is the first 6 weeks of treatment.

Table 5.11 Cohort de-escalation table during safety run-in:

Dose Level	Troriluzole Dose
Starting cohort	140 mg PO QAM and 280 mg PO QPM
Cohort -1	140 mg PO BID

Cohort -2	140 mg PO daily
If ≥ 2 DLTs on Cohort -2	Permanently stop the trial

During the induction phase:

Nivolumab (1 mg/kg) followed by ipilimumab (3 mg/kg) will be administered every 3 weeks, with 21 consecutive days defined as a treatment cycle. Troriluzole will be continuously self-administered orally twice a day (at the dose level indicated by participant's cohort).

During the maintenance phase:

Nivolumab (480 mg IV) will be administered every 4 weeks, with 28 consecutive days defined as a treatment cycle. Troriluzole will be continuously self-administered orally twice a day (at the dose level indicated by participant's cohort).

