13.2 Sample Size, Accrual Rate and Study Duration

Accrual Targets				
Ethnic Category	Sex/Gender			
	Females		Males	Total
Hispanic or Latino	1+		2=	3
Not Hispanic or Latino	39+		66=	105
Ethnic Category: Total of all subjects	40+		68=	108
Racial Category				

American Indian or Alaskan Native	0+	0=	0
Asian	1+	2=	3
Black or African American	0+	0=	0
Native Hawaiian or other Pacific Islander	0+	0=	0
White	39+	66=	105
Racial Category: Total of all subjects	40+	68=	108

Sample Size. The total sample size for this investigation is between 6 and 108 patients, which includes 6 - 18 patients in the safety run-in, and up to 90 patients in the randomized portion.

Sample size estimates for the randomized trial are based on a proportional hazards mixture cure model with type-I error of 0.1, uniform accrual over 24 months, and 12 additional months of follow-up. The six-month global PFS proportion in the INP arm is assumed to be 0.6³ and follows an exponential distribution; it is also assumed that approximately 30% of patients in the INP arm and 50% of patients in the INT arm are cured (odds ratio = 2.33). Under these assumptions, there would be 80% power to detect a 6-month PFS rate of approximately 0.8 in the INT arm (hazard ratio = 0.557).⁴²

Accrual rate. Assuming accrual of about 3 patients per month across 6 sites and an equal allocation between experimental and control arms, 36 patients will be accrued within one year.

Study duration. Assuming unequal protocol activation times and holding accrual for analysis of safety run-in, study duration will be 4-5 years.

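### Expansion from three to six patients is written only for the starting dose, so read literally a fallback dose can become the MTD on 1 DLT in 3, at odds with the 3+3 label and the planned 6–18

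*Combined protocol and SAP*

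**What the plan says.** Section 1.1 sets the design: "There will be a Safety Run-in, which will be a single-arm, open-label 3+3 design". Sections 5.1.1 and 13.1 apply the same label to up to three cohorts: a starting dose of 140 mg/280 mg and two fallback doses, Cohort -1 and Cohort -2.

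Section 5.1.1 gives the operating rule.

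- Review point: "At the end of each cohort accrual of 3 participants, enrollment will pause".
- With two or more DLTs, "the fallback dose in cohort -1 will be used for three new participants accrued to Cohort -1".
- With fewer than two in the first three, "an additional three participants will be added to the starting cohort".
- Then: "From this point, if fewer than two patients within a cohort have DLTs then that dose level will be considered the MTD".

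No sentence expands Cohort -1 or Cohort -2. Section 13.1 restates the MTD rule without the expansion and without a cohort size: "If fewer than two patients within a cohort have DLTs then that dose level will be considered the MTD". Section 13.4 gives the safety review three outcomes: declare an MTD, change the dose, or stop enrolling. Expanding a cohort is not among them.

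Section 13.2 gives the size: "The total sample size for this investigation is between 6 and 108 patients", "which includes 6 - 18 patients in the safety run-in", with up to 90 more in the randomized part.

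**The concern.** As worded, the two kinds of dose level are held to different standards. At the starting dose 2 DLTs in 6 (33%) is a failure. At a fallback dose 1 in 3 (also 33%) is a pass. The looser standard applies just after a higher dose has proved too toxic.

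Failure of the starting dose is not remote. Section 2.4 reports that dose as the MTD with nivolumab alone; here ipilimumab is added. Section 2.5 quotes grade 3–4 toxicity of 55% for the two checkpoint inhibitors together. Section 6.7 says that shared events such as raised liver tests, nausea and diarrhea should in most cases be attributed to all three drugs. Section 6.2 counts a grade 3 or higher event in the first six weeks as a DLT if it is at least possibly related to troriluzole.

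The dose chosen in the run-in is the one given in the randomized part. If it rests on three patients with one DLT, the evidence for its tolerability is thin.

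**Working it through.** **1. The planned run-in size.** I followed every path through the three dose levels and added up the patients, with no replacements.

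| Rule | Possible totals |
|---|---|
| 5.1.1 as worded: 3 or 6 at the starting dose, 3 at each fallback dose | 6, 9, 12 |
| 13.1 alone, cohorts of three | 3, 6, 9 |
| Expansion at every dose after 0 or 1 DLT in 3 | 6, 9, 12, 15, 18 |
| 5.1.1 at the starting dose, conventional 3+3 at fallback doses (0/3 passes, 1/3 expands) | 6, 9, 12, 15, 18 |
| Conventional 3+3 throughout | 3, 6, 9, 12, 15, 18 |

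The 6–18 of section 13.2 is reproduced only by the two rules in which the starting dose always needs six and a fallback cohort can expand. Then 18 + 90 = 108. As worded, the largest run-in is 6 + 3 + 3 = 12, and 12 + 90 = 102.

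**2. What a pass shows.** The highest DLT proportion that passes is 1/6 (17%) at the starting dose and 1/3 (33%) at a fallback dose. The exact one-sided 95% upper bound for the DLT rate is 86% after 1/3 and 58% after 1/6.

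**3. How often the difference would matter.** The documents state no DLT rate, so the rates p below are assumptions. The probability of at most one DLT in n patients is A(n) = (1−p)^n + n·p·(1−p)^(n−1). Stopping after two DLTs in the first three does not change A(6).

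| Fallback rate p | A(3) | A(6) | A(3) − A(6) | 1/3 seen, then at least one more in the next three |
|---|---|---|---|---|
| 0.1 | 0.972 | 0.886 | 0.086 | 0.243 × 0.271 = 0.066 |
| 0.2 | 0.896 | 0.655 | 0.241 | 0.384 × 0.488 = 0.187 |
| 0.3 | 0.784 | 0.420 | 0.364 | 0.441 × 0.657 = 0.290 |

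Column four is the wrong-acceptance probability if six are always required. Column five is the same quantity if only 1/3 triggers expansion. Both must be multiplied by the probability that the starting dose fails, 1 − A(6): 0.345 at a starting rate of 0.2 and 0.580 at 0.3.

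| Starting rate, fallback rate | Six always required | Only 1/3 expands |
|---|---|---|
| 0.2, 0.1 | 0.345 × 0.086 = 3% | 0.345 × 0.066 = 2% |
| 0.3, 0.1 | 0.580 × 0.086 = 5% | 0.580 × 0.066 = 4% |
| 0.2, 0.2 | 0.345 × 0.241 = 8% | 0.345 × 0.187 = 6% |
| 0.3, 0.2 | 0.580 × 0.241 = 14% | 0.580 × 0.187 = 11% |
| 0.3, 0.3 | 0.580 × 0.364 = 21% | 0.580 × 0.290 = 17% |

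**4. Extra patients if six are required at every dose, given that the starting dose fails.** The wording as it stands uses 3 + 3·(1 − A(3)) fallback patients on average: 3.31 at p = 0.2 and 3.65 at p = 0.3. Requiring six uses [6 − 3·(1 − A(3))] × [1 + (1 − A(6))]: 5.688 × 1.345 = 7.65 and 5.352 × 1.580 = 8.46. The difference is 4.3 to 4.8 patients. At three patients per DLT period, that is 1.4 to 1.6 periods.

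**The case against.** The strongest reply is that the plan already implies the expansion. The 3+3 label covers all cohorts. In 5.1.1 the opening words of the MTD sentence, "From this point, if fewer than two patients within a cohort have DLTs then that dose level will be considered the MTD", can be read as taking effect only after expansion. The minimum of 6 in 13.2 shows that 13.1 cannot be read alone, since alone it would let the starting dose pass on three. This stands as evidence of intent. It does not supply the rule: the only expansion written before that sentence is of the starting cohort, and 13.1 drops the opening words. The label cannot fill the gap either, because 5.1.1 is not a conventional 3+3: it expands after 0 in 3 as well as after 1 in 3.

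Second, a reader might infer that six per dose was certainly intended, so that accepting 0 in 3 at a fallback dose is also an error. The documents do not settle that. Conventional 3+3 at the fallback doses reproduces 6–18 equally well, and under it only the 1-in-3 path is at fault.

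Third, controls lie on this path. Enrollment pauses for review (13.4), a lowered MTD requires an amendment (5.1.2), the DSMC oversees the run-in (12.2.2), and individual doses can be reduced (6.3). In the randomized part there is a stopping boundary, for neurotoxicity only (13.4). These make unexamined acceptance of 1 in 3 less likely. None of them requires six patients at a fallback dose.

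Fourth, the larger probabilities assume that the lower dose is nearly or equally as toxic as the one that failed. That is fair, and the rows with a fallback rate of 0.1 show how far the figures drop.

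**Conclusion.** The point holds as a gap in the written rule and an inconsistency with the plan's own label and run-in size. Followed literally, the text accepts a fallback dose on 1 DLT in 3 and yields 6, 9 or 12 run-in patients.

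A reader might go further and conclude that the 18 and the 108 are wrong. The documents do not support that: both figures are right once fallback cohorts can expand, so the error lies in the rule. Nor does the gap touch the primary analysis, its type I error or the 90 randomized patients.

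The consequence arises only if the starting dose fails. At assumed DLT rates the overall probability of accepting Cohort -1 on three patients when expansion would have rejected it is about 3–5% at a fallback rate of 0.1 and 8–21% at 0.2–0.3 if six are always required. If only 1 in 3 triggers expansion, it is about 6–17% at 0.2–0.3. The text should be corrected, because a dose-selection rule for a new triplet should not depend on inference.

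**What to change.** In 5.1.1, write the rule once for all doses, for example: *At each dose level, if fewer than 2 of the first three participants have a DLT, three more are added at that dose level. The dose is the MTD only if fewer than 2 of the six have DLTs. If 2 or more have DLTs at any point, three new participants are enrolled at the next lower dose, or, at Cohort -2, the trial stops.* Repeat it in 13.1, and add expansion of the cohort to the review options in 13.4. If the sponsor prefers conventional 3+3 at the fallback doses, the minimum is that 1 DLT in 3 there must trigger expansion to six.

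Keep 6–18 in 13.2 as enrolled patients without replacement. Sections 5.1.1 and 13.1 count a participant as having completed the DLT period without DLT only if at least 80% of troriluzole doses were taken, but no replacement rule is written. If participants not evaluable for DLT are to be replaced, say so and note that the run-in may then exceed 18 and the total 108.

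The cost is nil if the starting dose passes. If it fails, requiring six at every dose adds 0, 3, 6 or 9 run-in patients and 0 to 3 six-week DLT periods compared with the present wording, always within the 18 planned when there are no replacements. The largest addition arises when the present wording would accept Cohort -1 at 6 or 9 patients, but under the fix that cohort fails on expansion and Cohort -2 takes six (15 or 18).
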